Chronic HBV (CHB) is an emerging health crisis in the US. Approximately 15%-40% of those with chronic HBV will develop serious liver diseases during their lifetime including decompensated cirrhosis and hepatocellular carcinoma (HCC).^{4, 9-11} Asian Americans (AA) have the highest liver cancer mortality rates and the highest prevalence of CHB.¹² Further, inadequate disease monitoring and care will contribute to poorer outcomes and increased healthcare costs. Indeed, the soaring medical costs associated with HBV infection are estimated to be as high as \$1.5 billion each year.^{1, 13-15}

Early monitoring and adherence to recommended HBV disease management guidelines improves health outcomes, prevents expensive complications such as cancer treatments or liver transplants, and reduces premature deaths.^{1, 11, 15, 16-20}

Despite the health and economic advantages of early monitoring and regular follow up care for HBV, few people are receiving such care. One study indicated that fewer than 50,000 US HBV patients have sought early treatment for HBV, meaning that less than 10% of those eligible for treatment actually receive monitoring and regular follow up care.²⁰ Asian Americans with CHB may not seek care because they “feel well”^{21, 22}, have lower access to care (e.g., no regular healthcare provider, need for English translator), face more economic (e.g., lack of health insurance, low income) and cultural barriers (e.g., negative perceptions of Western medicine, stigma of HBV disease), or have a low level of knowledge about HBV and the benefits of care.^{21, 23-29} Even among Asian American CHB patients receiving care, adherence to monitoring and treatment guidelines is low as 40%-53% at 12 month follow-up.^{21, 30}

2. Significance of the Proposed Study:

CHB is a major contributor to the racial/ethnic health gap and HBV disparities in mortality between AAs and Whites are widening.^{6, 12} Early monitoring and adherence to recommended CHB management guidelines are an essential part of a comprehensive approach to improving CHB control for reducing incidence and mortality rates of liver cancer.^{1, 7, 21-23, 31, 32-35} Patient adherence to regular follow up tests every 6 and 12 months is associated with optimal CHB control.¹¹ Unfortunately, early onset of liver problems comes without apparent symptoms and only consistent follow-up testing allows for early treatment. However, adherence rates to monitoring guidelines are poor among AA CHB patients.

This application provides a unique opportunity to address these gaps in the literature and respond to this critical health disparity issue by investigating a Patient Navigator-led Text Messaging Intervention (PMNI).

II. OBJECTIVES

The described study is a collaborative effort between the lead agency, Center for Asian Health of Temple University and its long-term clinical partners in greater Philadelphia area and New York city.

III. STUDY DESCRIPTION

1. Overview of Study Design

Patient-centered and community-based participatory research approach will be applied to the randomized comparative trial design, a range of quantitative and qualitative evaluation methods, and implementation of a HBV intervention to improve care for underserved AA chronic HepB patients. Temple U. Center for Asian Heath (CAH) partnered with Federally Qualified Community Health Center (FQHC) and community primary care clinics that serve low-income Chinese, Korean and Vietnamese patients to conduct a comparative trial to evaluate the effectiveness of the patient navigator-led plus mobile phone text messaging intervention (PNMI), an interactive patient-centered culturally and linguistically appropriate approach. The study builds on a strong foundation of 20-year clinic-community-academic partnership. As shown in our pilot studies, CBPR approach were applied to engage patient partners and stakeholders in project planning, recruitment, delivery, evaluation and dissemination.

The proposed study is a 2-arm randomized comparative trial with individual patients as the unit of randomization. Bilingual patient navigators will be recruited and trained to deliver the PNMI intervention to help patients improve adherence to HBV monitoring tests on time.

2. Selection of Patient Participants

Inclusion Criteria: Patients (N=500) will be included in the study if they meet the following criteria:

- self-identified Chinese, Korean and Vietnamese ethnicity (these three Asian subgroups consist of the largest number of immigrants from countries with high prevalence of HBV infection,
- age 18 and above
- not enrolled in any chronic HBV adherence management intervention (to prevent a potential program impact),
- medically diagnosed chronic HBV infection with positive for hepatitis B surface antigen (HBsAg) for more than six months, and
- not had HBV monitoring tests for more than six months.

Exclusion Criteria: Patients will be excluded from the study for the following conditions:

- diagnosed with cirrhosis, hepatocellular carcinoma, liver failure and liver cancer (The purpose of regular follow up tests is to detect early signs of CHB

complications). Monitoring the progression of CHB complications is different in schedules and tests),

3. Intervention Procedures

- 1) Study Timeline
- **The duration of the project**
1/1/2015-12/31/2017
- **The duration of a subject's participation in the study.**
12-13 months
- **The duration anticipated to enroll all subjects.**
12 months
- **The estimated date that the investigators will complete the study.**
December 31, 2017

2) Intervention delivery

Following randomization, intervention patients will receive PNMI in-person education sessions from patient navigators who navigate patients through the program. PNMI focuses on recognizing patients as active participants in their own health care. PNMI intervention bilingual patient navigator-led HBV management; text messaging; clinical support assistance and HBV management education visual aids.

4. Statistical considerations

Data Analysis Plan

The primary outcome analysis will calculate the difference in adherence rates between two groups (PNMI – SC) at 6m or 12m post-intervention. Bonferroni multiple comparison adjustment will be used for two primary hypothesis tests. The difference of two binomial proportions and its 97.5% (due to Bonferroni adjustment) 2-sided confidence interval (C.I) will be calculated for inference. We expect the tests for intervention effects for both 6m and 12m post intervention will be highly significant with effect size substantially larger than 20%, based on our pilot study data and other screening studies. Though not a primary hypothesis, we will examine if the adherence rate has declined at 12m from that at 6m by calculating a 95% C.I for the difference of two rates. If the decline is statistically significant, a booster intervention after 6m post intervention may be needed for future disseminations. To control for known and postulated factors, a number of variables will be included as covariates in most analyses, including (1) race, (2) clinics, (3) education, (4) age, (5) gender, (6) time living in U.S., (7) birthplace, and (8) English proficiency

5. Withdrawal of Subjects

If a participant to be found out with conditions meeting any of the exclusion criteria, she/he will be withdrawn from the research because the medical procedures of those conditions are very different with the purpose of proposed study. There will not be any consequences for participants if they decide to withdraw from any phase of our project.

6. Privacy & Confidentiality

All collected data will be used solely for the purpose of the research study and treated with full confidentiality. Specifically, each participant will be assigned an ID number, which will be used in place of her/his name. The data will be kept on computers, which will only be used by project research team staff. All study team staff computer is locked by unique user name and password. Questionnaires will be stored in a locked office where only project staff will be permitted to view questionnaire contents. Computer research data will not have participants' private information.

7. Risks to Subjects

We do not anticipate major risks for study participants. The study participants of both intervention and comparison groups will receive medical care for HBV monitoring. There may be psychological response to some participants because of possible worsen test results from HBV monitoring status. However, the long-term benefits of early detection of HBV progression status are much greater than the psychological and emotional trauma may be precipitated by a test results. In contrast, these participants can be alerted by those results and take early action for necessary medical care. The PI and study team members and collaborating health providers will provide adequate counseling and assistance to participants.

No potential long-range risks are anticipated as a result of this research project.

We do not anticipate major risks for study participants. The PI and her team members and collaborating health providers will provide adequate counseling and assistance to participants. In addition, all collaborating clinical partners have capacity to support subjects if there are any needs as result of anticipated consequences of participation in the research.

8. Potential Benefits to Subjects

The purpose of this study is to improve HBV routine/regular monitoring adherence. Subjects in intervention group of this study will receive education on knowledge about HBV monitoring and navigation assistance for their further medical care needs. Participants in comparison group will also receive standard care for their routine HBV care. Stay with adherence of HBV monitoring is a critical practice to ensure early detection of HBV progression and capture the right momentum of early treatment for HBV.

9. Informed Consent

The consent process will be taken place on site of collaborating clinical partners and CBOs located in greater Philadelphia area and New York City. Project staff will inform participants of the nature and purpose of the study as well as participant rights. A consent and HIPPA form will be provided to participants prior to participation in the study. Participants will be informed about the purpose and nature of the study, intervention and comparison contents of the project, foreseeable risks, benefits of participation and right of participants, confidentiality statement, voluntary participation statement, and institutional IRB contact and research contact. Participants will be encouraged to contact the PI or IRB regarding any concerns about component of the study. Participants are also informed that they may choose withdrawing at any time during the study without penalty.

10. Data Safety and Monitoring

To ensure all regulatory requirements of PCORI are met, a Data Safety Monitoring Committee consists of five individuals who are expert in the study areas and who are familiar with the community but having no conflict of interest with the proposed project.

The Monitoring Committee will meet in person or teleconference two times a year over the course of the study, or at an intermediate time, if needed, in response to immediate needs/concerns on IRB related issues, implementation of protocol, and any unanticipated problems.

11. Adverse Event Reporting

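### The primary difference in adherence rates is written unadjusted and no listed covariate measures prior monitoring, so a modest gain in precision goes unused.

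*Combined protocol and SAP*

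**What the plan says.** - **Entry (III.2, Inclusion Criteria).** Patients qualify if they have "not had HBV monitoring tests for more than six months". The rule sets no upper limit and defines no strata.
- **Monitoring interval (Significance of the Proposed Study).** "Patient adherence to regular follow up tests every 6 and 12 months is associated with optimal CHB control".
- **Design (III.1).** The trial is a "2-arm randomized comparative trial with individual patients as the unit of randomization". No allocation ratio or stratification is stated. The sample size in III.2 is 500, without a derivation.
- **Primary analysis (III.4, Data Analysis Plan).** "The primary outcome analysis will calculate the difference in adherence rates between two groups (PNMI – SC) at 6m or 12m post-intervention". For inference: "The difference of two binomial proportions and its 97.5% (due to Bonferroni adjustment) 2-sided confidence interval (C.I) will be calculated for inference".
- **Covariates (III.4).** Eight variables are named for the majority of analyses: "1) race, (2) clinics, (3) education, (4) age, (5) gender, (6) time living in U.S., (7) birthplace, and (8) English proficiency". The list is introduced as non-exhaustive. The plan does not say whether the primary comparison is one of the adjusted analyses, and it gives no adjusted model.

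**The concern.** The outcome is adherence to monitoring tests, and every patient enters because of a lapse in those tests. The rule covers a patient just past six months as well as one untested for many years or never tested. How long someone has gone without a test is the baseline characteristic closest to the outcome, and it could plausibly predict who tests later under either arm.

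Randomisation balances lapse time on average, but the outcome variation that lapse time explains stays in the standard error of an unadjusted difference. Adjusting for it would narrow the interval without enrolling more patients. As written, the primary estimate adjusts for nothing, and the named covariates are demographic or background variables plus clinic. What is at stake is the width of the two 97.5% intervals, and power if the true effect is smaller than the plan expects.

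**Working it through.** **What can be reproduced from the plan.** III.4 states that "Bonferroni multiple comparison adjustment will be used for two primary hypothesis tests". With 0.05 overall, 0.05/2 = 0.025 per test, which is the stated 97.5% interval; the critical value is z = 2.241. The figure of 500 cannot be reproduced, because no power, standard-care (SC) rate, allocation ratio or dropout is given.

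**Inputs.** From the documents: 500 patients, two arms, two-sided alpha 0.025 per test, and an expected effect well above 20 points. Assumed, not in the documents:
- 1:1 allocation (250 per arm) with everyone analysed.
- SC adherence of 45%. The background section gives 40%-53% at 12 months for patients already in care, which need not apply to a lapsed population.
- Two equal lapse groups (share s = 0.5), an adherence gap g between them in both arms, and the same treatment effect in each group.

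**Formulas.**
- Unadjusted: V = pC(1 − pC) + pT(1 − pT), with variance of the difference V/250.
- Adjusted for lapse group: V_adj = V − 2·s(1 − s)·g².
- Power: Φ(effect / √(V/250) − 2.241), with V_adj in place of V after adjustment.
- Approximate proportional reduction: s(1 − s)g² / (0.45 × 0.55). For g = 0.30 this is 0.0225/0.2475 = 9.1%.

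**12-point effect (45% against 57%).** V = 0.2475 + 0.2451 = 0.4926, SE = √(0.4926/250) = 0.0444, and power = Φ(0.12/0.0444 − 2.241) = 68%.

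**20-point effect (45% against 65%).** V = 0.2475 + 0.2275 = 0.4750, SE = 0.0436, interval half-width 2.241 × 0.0436 = 9.8 points, and power 99.1%.

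| Gap between lapse groups | Variance reduction | Power, 12-point effect | Power, 20-point effect | Half-width, 20-point effect |
|---|---|---|---|---|
| No adjustment | – | 67.8% | 99.1% | 9.77 points |
| 10 points | 1.0% | 68.3% | 99.1% | 9.72 |
| 20 points | 4.0% | 69.8% | 99.3% | 9.56 |
| 30 points | 9.1% | 72.4% | 99.5% | 9.30 |
| 40 points | 16.2% | 76.2% | 99.7% | 8.91 |

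**Checks and sensitivity.**
- A simulation of the standardised risk difference (20,000 trials, 12-point effect) gave reductions of 3.7%, 9.0% and 15.0% for gaps of 20, 30 and 40 points, slightly below the formula at the top end.
- With a 30:70 split of lapse groups, the reductions are 0.8%, 3.4%, 7.6% and 13.6%.
- At an assumed 15-point effect, power is 87.6% unadjusted and 88.0%, 89.0%, 90.7% or 93.0% for the four gaps.
- Over SC rates of 10%-53% and a 20-point effect, unadjusted power is 98.9% or more with 250 per arm, and at least 96.4% with 200 analysed per arm.
- In sample-size terms, a 9.1% reduction corresponds to 500/(1 − 0.091) ≈ 550 patients analysed without adjustment.

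All reductions are relative to no adjustment. If other covariates are also adjusted for and overlap with lapse time, the additional gain from lapse time is smaller.

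**The case against.** The case against has several parts.

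1. **The covariate list does not drive the primary interval.** A reader might infer that leaving lapse time off the list is what costs precision. The text does not support that: the primary is a plain difference of two proportions, so a ninth item on the list would leave its interval unchanged. This stands, and it is why the estimator has to change too.
2. **The premise is untested.** The documents give no distribution of lapse times and no relation between lapse and later testing. This stands. Lapse time is a plausible predictor, not a demonstrated strong one, and at a 10-point gap the gain is negligible.
3. **The plan has power to spare.** At its own expected effect, adjustment adds less than one percentage point of power. This stands. The visible gain depends on a smaller effect, such as 12 points, which the documents do not propose. III.4 does, however, plan to examine whether adherence declines between 6 and 12 months, so a smaller 12-month effect is not far-fetched.
4. **The information is not quite free.** Eligibility strictly needs a yes or no on the six-month rule, not a date, and the date may be unknown or held by another provider. This stands in part: the cost is one field with some unknown entries.
5. **The covariate list is open-ended.** It could accommodate lapse time later. But choosing a covariate for the primary estimate after seeing data is weaker than naming it in advance, so this does not remove the case for prespecification.

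A reader might also infer bias, or a harm from chance imbalance in lapse time. Neither follows: the unadjusted comparison is unbiased under randomisation, and its interval already allows for chance imbalance.

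**Conclusion.** The point holds as a minor matter of efficiency. The entry rule can mix short and long lapses, the primary comparison is written without adjustment, and no named covariate captures prior monitoring. The available gain is a variance reduction of about 1% to 16%, conditional on the assumed gap of 10 to 40 points, equal lapse groups, 45% SC adherence and 250 analysed per arm. It changes almost nothing for the tests at a 20-point effect, where power is about 99% either way. It is worth up to about 8 points of power (68% to 76%) at an assumed 12-point effect with the largest gap. The documents do not show the trial to be biased, invalid or underpowered on this account.

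**What to change.** 1. When eligibility is checked, record time since the last HBV monitoring test, with categories for never tested and unknown.
2. Add this variable to the prespecified covariates in III.4.
3. State in III.4 that the primary difference in adherence rates at 6 and at 12 months, each with its 97.5% confidence interval, is a covariate-standardised risk difference that includes this variable. The estimate then remains a difference in adherence rates. Name the model and the full set of covariates in it.
4. Keep the unadjusted difference of two proportions as a sensitivity analysis.

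Cost: one screening-form field, some unknown dates, a short addition to the analysis plan, and a slightly more complex primary estimator. No extra patients or procedures are needed. The entry criterion and the clinical testing intervals stay unchanged.

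### Does timing the primary comparison from the intervention, which only one arm receives, give the two arms different observation windows?

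*Combined protocol and SAP*

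**What the plan says.** Section III.4 (Data Analysis Plan) defines the primary analysis as the difference in adherence rates between PNMI and standard care "at 6m or 12m post-intervention", and refers again to the "tests for intervention effects for both 6m and 12m post intervention". Each of the two comparisons gets a two-sided 97.5% confidence interval under a Bonferroni adjustment. The plan expects an "effect size substantially larger than 20" per cent. The same section will also examine whether adherence at 12 months has fallen from its 6-month level.

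On who receives what, Section III.3 says: "Following randomization, intervention patients will receive PNMI in-person education sessions". Section III.8 says: "Participants in comparison group will also receive standard care for their routine HBV care". Section III.1 describes a "2-arm randomized comparative trial with individual patients as the unit of randomization". The Study Timeline in Section III.3 gives one length of participation, 12-13 months, not split by arm. No section names the date from which 6 and 12 months are counted in the standard-care arm.

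**The concern.** A comparison of two proportions at a fixed time needs the same clock in both arms. Here the named starting event is the intervention, and standard-care patients have none. Read literally, the wording would allow observation to open at randomisation in both arms but close later in PNMI, because delivery takes time. PNMI patients would then have longer in which to be tested. Part of the primary difference would be extra observation time, which the 97.5% interval does not reflect, and the overall error rate that the Bonferroni adjustment is meant to hold would be exceeded.

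**Working it through.** **The plan's own figure.** Two tests at an overall 5% (implied by the adjustment, not stated) give 0.05/2 = 0.025 per test, hence 97.5% intervals with z = 2.2414. The stated level reproduces.

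**Inputs**
- From the documents: 500 patients (Section III.2, "Patients (N=500) will be included in the study"); 12-month adherence of 40-53% among patients already in care (background section).
- Assumed: 250 per arm with no loss; a constant testing rate; at least one test counts as adherent; no true effect; a PNMI window at most one month longer, reading 12-13 months as entry to the 12-month assessment.
- Also assumed: a lower 12-month rate of 20%. The trial enrols patients who have "not had HBV monitoring tests for more than six months", and no rate is stated for them.

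**Case A: the PNMI window is one month longer.** The rate after t months is 1 − (1 − p12)^(t/12). The half-width with matched windows is 2.2414 × √(2p(1 − p)/250).

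| p12 | 6 → 7 months (%) | Bias (points) | Half-width (points) | Per-test error |
|---|---|---|---|---|
| 20% | 10.56 → 12.21 | 1.65 | 6.16 | 0.051 |
| 40% | 22.54 → 25.77 | 3.23 | 8.38 | 0.082 |
| 53% | 31.44 → 35.62 | 4.18 | 9.31 | 0.106 |

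| p12 | 12 → 13 months (%) | Bias (points) | Half-width (points) | Per-test error |
|---|---|---|---|---|
| 20% | 20.00 → 21.47 | 1.47 | 8.02 | 0.037 |
| 40% | 40.00 → 42.50 | 2.50 | 9.82 | 0.050 |
| 53% | 53.00 → 55.87 | 2.87 | 10.01 | 0.057 |

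In simulation, the chance that at least one of the two intervals excludes zero is 0.08-0.14, against 0.04-0.05 with equal windows. With half a month the bias is 0.8-2.1 points at 6 months and 0.7-1.5 at 12, and that chance is 0.05-0.07. A longer standard-care window would reverse the sign.

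**Case B: windows of equal length, PNMI shifted by one month.** If any test counts, a constant rate gives zero bias. If only a first test counts, write S(m) = (1 − p12)^(m/12). The shortfall in PNMI is [1 − S(6)] − [S(1) − S(7)] = 0.19, 0.94 and 1.92 points at 6 months, and [1 − S(12)] − [S(1) − S(13)] = 0.37, 1.67 and 3.23 points at 12 months. This works against PNMI.

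**Case C: a common clock.** Zero offset, zero bias.

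**Does the Case A outcome fit the plan?** At least one test since time zero can only rise with time. The plan looks for a decline from 6 to 12 months, so its 12-month outcome cannot be that cumulative one. If it refers to a separate interval such as months 6-12 (an assumption, since adherence is not defined), that interval is six months long in both arms whatever the anchor, and the constant-rate model gives no bias at 12 months. Only the 6-month figures in Case A would remain; the joint chance would then be about 0.08-0.13.

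**Against the expected effect.** With 250 per arm, power at a true 20 points is 0.990 or more per test. At 10 points it is 0.507-0.809.

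**The case for a change.** The strongest case for acting is that the plan names the wrong event twice and never names the right one. Even within PNMI it is unclear whether the clock starts at the beginning or the end of delivery: the number of sessions is not given and the text messaging has no stated end. A test done between randomisation and the end of delivery could be counted or left out, and the choice might be made after data are seen. In Case A the chance of a false positive is up to about 2.9 times its equal-window value (0.139/0.047), and one sentence would settle the matter.

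It is true that no index date is stated for standard care and that the one-month bound rests on a reading of the participation length. The arithmetic is also right for the case it describes. But that case requires the window to open at randomisation in both arms and close later in one. Six months counted after an event more naturally describes a six-month window, which is Case B, with no bias or a bias against PNMI. Nothing in the documents sets different windows by arm: the plan applies one time label to a two-group contrast and one participation length to all patients.

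**Conclusion.** No change follows. The plan leaves the standard-care index date unstated, but that is missing detail and not a rule shown to give a wrong result. Individual randomisation supplies a date common to both arms, and an analyst would sensibly follow both from a common start for the same length of time. On that reading the bias is zero.

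If, and only if, the PNMI window were one month longer, the 6-month difference would be overstated by about 1.6-4.2 points, which is 0.27-0.45 of the matched half-width. That rests on 250 per arm, a constant testing rate, any one test counting, and a 12-month rate of 20-53%, of which the 20% is assumed. The 12-month figure of 1.5-2.9 points also needs a cumulative outcome, which the planned look for a decline contradicts. At the expected effect above 20 points the conclusion would stand and only the estimate would move. A true effect nearer 10 points would leave less margin, but still only if the windows really differed, which the documents do not show.

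### Single-step Bonferroni on the 6-month and 12-month primary tests is valid, but Holm controls the same 5% familywise error, is never less powerful, and helps noticeably only if the 12-month effect is well below the plan's expectation

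*Combined protocol and SAP*

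**What the plan says.** Section III.4 (Statistical considerations, Data Analysis Plan) defines the primary analysis as the "difference in adherence rates between two groups (PNMI – SC) at 6m or 12m post-intervention". On multiplicity it says "Bonferroni multiple comparison adjustment will be used for two primary hypothesis tests". The decision rule is the interval: "The difference of two binomial proportions and its 97.5% (due to Bonferroni adjustment) 2-sided confidence interval (C.I) will be calculated for inference". No step-down, gatekeeping or fixed-sequence rule appears, so this is single-step use at a fixed level for each test.

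The same paragraph expects the tests of "intervention effects for both 6m and 12m post intervention will be highly significant with effect size substantially larger than 20" percent. As a separate question, expressly not a primary hypothesis, "we will examine if the adherence rate has declined at 12m from that at 6m by calculating a 95% C.I". The only sample-size figure is in the inclusion criteria: "Patients (N=500) will be included in the study if they meet the following criteria". The documents give no power calculation, control rate for design, allocation ratio or allowance for loss.

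**The concern.** Single-step Bonferroni does not reuse the error allowance that becomes free once one hypothesis has been rejected. Suppose 6 months is clearly positive and the 12-month p-value falls between 0.025 and 0.05. The plan would report 12 months as not significant. Holm would declare it significant under the same 5% familywise limit and with no assumption about the correlation between the two time points.

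The pattern that loses most is a strong early effect followed by a weaker later one. Nothing in the documents shows how well the 12-month test would fare if the expected effect proved optimistic.

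**Working it through.** **The plan's own figure.** Two tests sharing 5% give 0.05/2 = 0.025 each, and 1 − 0.025 = 97.5%. This matches the stated interval exactly.

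**Inputs**
- From the documents: N = 500, two arms, two-sided 0.025 per test, and an expected effect above 20%, read as percentage points because the analysis is a difference of proportions.
- Assumed: 1:1 allocation (250 per arm), and control adherence of 40% to 53%, which the background section gives for 12-month adherence and which is not a design input. The table uses 45%.
- Assumed: a 6-month effect of 20 points and a range of 12-month effects.

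**Formulas**
- SE = √{[p₀(1−p₀) + p₁(1−p₁)]/n} and m = d/SE, where d is the 12-month effect.
- Bonferroni power at 12 months ≈ Φ(m − 2.241).
- Power at level 0.05 ≈ Φ(m − 1.960). This is the ceiling for Holm, reached if 6 months always passes.
- If the two tests were independent, Holm gain = (ceiling − Bonferroni) × P(6 months passes at 0.025).

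For a 20-point effect at 6 months, SE = √[(0.2475 + 0.2275)/250] = 0.0436 and m = 4.588. So P(passes) = Φ(2.347) = 99.1%, and Holm almost reaches its ceiling.

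**Power at 12 months, 250 per arm, control 45%**

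| 12-month effect (points) | SE | m | Bonferroni | Level 0.05 | Holm gain (points) |
|---|---|---|---|---|---|
| 20 | 0.0436 | 4.588 | 99.1% | 99.6% | 0.5 |
| 17.5 | 0.0439 | 3.986 | 95.9% | 97.9% | 1.9 |
| 15 | 0.0442 | 3.397 | 87.6% | 92.5% | 4.8 |
| 12 | 0.0444 | 2.703 | 67.8% | 77.1% | 9.2 |
| 10 | 0.0445 | 2.247 | 50.2% | 61.3% | 11.0 |

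Simulating the two test statistics with correlation up to 0.5 changes these gains by about 0.1 point. Control rates of 40% and 53% give nearly the same gains.

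**Peak.** The gap between the two power curves is largest at m = (2.241 + 1.960)/2 = 2.10. There it equals 2Φ(0.1407) − 1 = 11.2 points, so the gain cannot exceed about 11. It reaches 5 points only for 12-month effects of about 4 to 15 points.

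**If 6 months is as weak as 12 months.** Under independence the gain at 15 points is (92.5 − 87.6) × 0.876 = 4.3, and at 12 points (77.1 − 67.8) × 0.678 = 6.3. With correlation 0.5 these fall to about 3.5 and 5.3.

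**With an assumed 20% loss** (500 × 0.8/2 = 200 per arm), the gains at 20, 17.5, 15, 12 and 10 points are about 1.5, 3.8, 7.0, 10.3 and 10.8. The range giving at least 5 points widens to about 4 to 17.

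**Error rates.** If neither effect exists, both methods reject something only when the smaller p-value is below 0.025. Their familywise error is therefore identical: 1 − 0.975² = 4.9% under independence, and 4.7% and 4.0% in simulation at correlations 0.5 and 0.8. If the 6-month effect is 20 points and the 12-month effect is nil, the 12-month false-positive rate is 2.5% under Bonferroni and about 2.5% + 2.5% × 0.991 = 5.0% under Holm.

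**The case against.** The strongest reply is that nothing is broken. The "97.5% (due to Bonferroni adjustment) 2-sided confidence interval" is the plan's decision rule, and two such intervals have at least 95% joint coverage, so test and interval always agree. Holm has no simple fixed-level interval to match. A statistician who values that agreement can reasonably prefer Bonferroni. This stands as a real trade-off. It can be managed by keeping the 97.5% intervals and stating that the significance decision follows Holm.

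The second reply is that at the plan's own expectation the gain is negligible. This also stands: with 20 points at both times, Bonferroni already gives about 99% power.

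A reader might infer that the plan itself foresees the effect waning, since "we will examine if the adherence rate has declined at 12m from that at 6m". The text does not support that. It concerns the adherence rate and gives no size. Both arms could decline together and leave the between-group difference unchanged, and the question has its own 95% interval, which the Bonferroni adjustment does not touch.

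Finally, the word "or" in the definition of the primary outcome leaves open whether success needs one positive test or both. If both were required, no split of the error rate would be needed and the choice between the two methods would not arise.

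**Conclusion.** The point holds as an optional efficiency gain. The Bonferroni adjustment is valid and correctly computed. Holm is at least as powerful in every case at the same familywise error.

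A reader might conclude that any shrinkage of the effect after 6 months costs 5 to 10 points of power, or that Holm is strictly better everywhere. Neither follows. A modest fall to 17.5 points costs only about 2 points at 250 per arm. A material gain needs a 12-month effect of roughly 15 points or less, and the full size also needs a strong 6-month result. No figure in the documents supports those values; they are my assumptions, as are the allocation ratio, the control rate and the loss. The case for acting is the low cost and the absence of any power calculation showing that the 12-month test is safe if the expected effect is optimistic.

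**What to change.** Before any outcome data by arm are examined, replace the multiplicity sentence in Section III.4 with:

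> The two primary hypotheses (6m and 12m) will be tested with the Holm step-down procedure: the smaller p-value at two-sided 0.025 and, if significant, the larger at two-sided 0.05. 97.5% CIs will be reported as simultaneous intervals, and the significance decision follows Holm.

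In the same edit, state whether success requires one or both time points.

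The change needs no extra patients or data. It has three costs to record:
- An endpoint can be declared positive while its 97.5% interval includes zero, so the report must say which rule decides.
- The chance of a false 12-month claim when 6 months is truly positive roughly doubles, to the 5% familywise limit.
- A 6-month p-value between 0.025 and 0.05 cannot be settled until the 12-month result is known.
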